7.2 Adverse Event Characteristics

- **CTCAE term (AE description) and grade:** The descriptions and grading scales found in the revised NCI Common Terminology Criteria for Adverse Events (CTCAE) version 4.0 will be utilized for AE reporting. All appropriate treatment areas should have access to a copy of the CTCAE version 4.0. A copy of the CTCAE version 4.0 can be downloaded from the CTEP web site:
http://ctep.cancer.gov/protocolDevelopment/electronic_applications/ctc.htm.
- **For expedited reporting purposes only:**
 - AEs for the agent(s) that are listed above should be reported only if the adverse event varies in nature, intensity or frequency from the expected toxicity information which is provided.
 - Other AEs for the protocol that do not require expedited reporting are outlined in the next section (Expedited Adverse Event Reporting) under the sub-heading of Protocol-Specific Expedited Adverse Event Reporting Exclusions.
- **Attribution of the AE:**
 - Definite – The AE is *clearly related* to the study treatment.
 - Probable – The AE is *likely related* to the study treatment.
 - Possible – The AE *may be related* to the study treatment.
 - Unlikely – The AE is *doubtfully related* to the study treatment.
 - Unrelated – The AE is *clearly NOT related* to the study treatment.

7.3 Expedited Adverse Event Reporting

7.3.1 For MCC Investigator-Initiated Trials (IITs), investigators **must** report to the Overall PI any serious adverse event (SAE) that occurs after the initial dose of study treatment, during treatment, or within 30 days of the last dose of treatment on the local institutional SAE form. This applies to the following categories:

- **Grade 3 (severe) Medical Events** – Only events that are Unexpected and Possibly, Probably or Definitely Related / Associated with the Intervention.
- **ALL Grade 4 (life threatening or disabling) Medical Events** – Unless expected AND specifically listed in protocol as not requiring reporting.
- **ALL Grade 5 (fatal) Events** regardless of study phase or attribution.

Note: If subject is in Long Term Follow Up, death is reported at continuing review.

Note: Abnormal laboratory values are not considered medical events, unless determined to be causative of SAE by the investigator or grade 5.

7.3.2 Required Forms and Reporting Structure for Clinical Trials

The following table outlines the required forms and reporting structure for clinical trials.

Study type	Expedited reporting to MCC	Expedited reporting to External Agency	Non-expedited AE	Form	IRB
IIT by MCC investigator of commercially available agent (non-IND and non-IDE)	
 • Grade 3 – Unexpected AE PLUS Possibly, Probably or Definitely Related • ALL Grade 4 Unless expected AND listed in protocol as not requiring reporting. • ALL Grade 5 (fatal) Events 	
FDA: Suspected AE that is serious and Unanticipated (not listed in IDB or consent)
	OnCore and DSMC reporting only	
Voluntary Medwatch 3500 for Serious and unanticipated
 
OnCore for all AEs, including SAEs
	Per IRB regulations

7.3.3 MCC Expedited Reporting Guidelines for MCC IITs

Investigators within MCC will report SAEs directly to the MCC DSMC per the MCC DSMC SOP and the University of Kentucky IRB reporting policy.

Attribution	MCC Reportable AEs				
	Gr. 2 & 3 AE Expected	Gr. 2 & 3 AE Unexpected	Gr. 4 AE Expected	Gr. 4 AE Unexpected	Gr. 5 AE Expected or Unexpected
Unrelated	Not required	Not required	5 calendar days [#]	5 calendar days	24 hours*
Unlikely					
Possible					
Probable		5 calendar days	5 calendar days [#]	5 calendar days	24 hours*
Definite	Not required				

If listed in protocol as expected and not requiring expedited reporting, event does not need to be reported.

* For participants enrolled and actively participating in the study *or* for AEs occurring within 30 days of the last intervention, the AE should be reported within 24 business hours of learning of the event.

7.3.4 Protocol-Specific Expedited Adverse Event Reporting Exclusions

For this protocol only, lymphopenia Grade 3 and Grade 4 does not require expedited reporting to the Overall PI or the MCC DSMC. It will not be recorded on the OnCore case report forms but will be recorded in the source documents.

7.4 Expedited Reporting to External Agencies

The Overall PI will comply with the policies of all external funding agencies and the UK IRB regarding expedited reporting, as per the UK IRB's SOP:

http://www.research.uky.edu/ori/SOPs_Policies/C4-0150-Mandated_Report_to_External_Agencies_SOP.pdf.

7.5 Expedited Reporting to Hospital Risk Management

Participating investigators will report to the UK Office of Risk Management any participant safety reports or sentinel events that require reporting according to institutional policy.

7.6 Routine Adverse Event Reporting

All Adverse Events **must** be reported in routine study data submissions to the Overall PI on the OnCore case report forms, except exclusions listed in the table below:

Adverse Event	Grade	Attribution
Alopecia	All	All causes
Lymphopenia	1-4	All causes
Laboratory abnormalities	1-2	Deemed not clinically significant by treating MD

AEs reported through expedited processes (e.g., reported to the IRB, FDA, etc.) must also be reported in routine study data submissions.

7.4 Second Malignancy

A second malignancy is one unrelated to the treatment of a prior malignancy (and is **NOT** a metastasis from the initial malignancy). Second malignancies require **ONLY** routine AE reporting unless otherwise specified.

8. PHARMACEUTICAL INFORMATION

A list of the adverse events and potential risks associated with cisplatin administered in this study can be found in Section 7.1.

8.1 Cisplatin

Refer to the package insert for detailed pharmacologic and safety information. Formulation: Each vial contains 10 mg of DDP, 19 mg of sodium chloride, 100 mg of mannitol, and hydrochloric acid for pH adjustment. One vial is reconstituted with 10 ml of sterile water. The pH range will be 3.5 to 4.5. Cisplatin injection also is available from the manufacturer in aqueous solution, each ml containing 1 mg cisplatin and 9 mg NaCl and HCl or NaOH to adjust pH.

Storage and Preparation: The dry, unopened vials should be stored at refrigeration temperature (+4°C to +8°C). Reconstitution results in a solution stable for not more than one hour at room temperature when exposed to normal room illumination, and not more than 8 hours at room temperature when protected from light.

Mechanism of Action: The dominant mode of action of cisplatin appears to be inhibition of the incorporation of DNA precursors, although protein and RNA synthesis are also inhibited. Although this drug seems to act as an alkylating agent, there are data to indicate that its mode and sites of action are different from those of nitrogen mustard and the standard alkylating agents.

Administration: After administering appropriate antiemetics, cisplatin will be infused over 1 hour according to institutional guidelines along with vigorous hydration of normal saline of 1 liter before and after cisplatin infusion.

Storage and Stability: Reconstituted solution of cisplatin is stable for 20 hours when stored at 27°C and should be protected from light if not used within 6 hours. The vials and injection should not be refrigerated. Cisplatin has been shown to react with aluminum needles, producing a black precipitate within 30 minutes.

Supply: Cisplatin is commercially available. The use of drug(s) or combination of drugs in this protocol meets the criteria described under Title 21 CFR 312.2(b) for IND exemption.

Chemotherapy Pharmaceutical Data: Cisplatin (Cis-Diaminedichloroplatinum, DDP)

9. BIOMARKER, CORRELATIVE, AND SPECIAL STUDIES

9.1 Correlative Studies: Functional Assessment of Cancer Therapy

Cognitive Function (FACT-Cog)[28] is a self-report questionnaire designed to assess perceived cognitive impairments (20 items), impact on quality of life (4 items), comments from others (4 items), and perceived cognitive abilities (9 items). Estimated time for administration is approximately 12 minutes.

9.2 Biologic Correlates

Protocol #: MCC-16-HN-29

Version Date: April 30, 2018

Serum studies in the proposed project will include measurement of the serum cytokine TNF- α , protein carbonyls, nitric oxide and 4-hydroxynonenal protein adducts. Additionally, we will also collect PK samples on a small cohort of these patients for cisplatin pharmacokinetics. Please refer to the Lab Manual for all instructions for correlative collection and processing.

10. STUDY CALENDAR

Baseline evaluations are to be conducted as follows:

- Within 3 weeks prior to registration: Complete history, physical examination, and evaluation of ECOG Performance Status, CBC; serum chemistry tests to include alkaline phosphatase, creatinine, electrolytes, AST (SGOT), and total bilirubin.
- All radiographic studies should be completed within:
 - Cohort 1: 6 weeks prior to registration
 - Cohort 2: 8 weeks prior to registration
- In the event that the patient's condition is deteriorating, laboratory evaluations should be repeated within 48 hours prior to initiation of the next cycle of therapy.

Pre-Study	Wk 1	Wk 2	Wk 3	Wk 4	Wk 5	Wk 6	Wk 7	Post Treatment Follow up	Long term Follow up ^b
Cisplatin Arm 1	A			A			A		
Cisplatin Arm 2	B	B	B	B	B	B	B		
Informed consent	X								
Demographics, medical history	X								
Concurrent meds		X ⁱ							
Physical exam	X	X		X			X	X	X ^h
Pulse, blood pressure	X	X		X			X	X	
Height	X								
Weight ^a	X	X	X ^a	X ^a	X	X ^a	X ^a	X	
Performance status	X	X						X	
CBC w/diff, plts ^a	X	X	X ^a	X ^a	X	X ^a	X ^a	X	X
Serum basic chemistry ^b			X ^a	X ^a		X ^a	X ^a		
Serum comprehensive chemistry ^c	X	X		X			X	X	
Adverse event evaluation		X-----							X
Tumor measurements	X ^d							X ^e	X ^e
B-HCG	X ^f								
Correlative studies		X							
FACTHN and FACT-COG ^g	X ^g						X ^g	X ^g	

A: Arm 1: Cisplatin 100 mg/m² every 3 weeks for 3 total doses

B: Arm 2: Cisplatin 40 mg/m² every week for 7 total doses

a: Every 3 weeks for Arm 1 during radiation, weekly for Arm 2 during radiation, and then as scheduled.

b: Weeks 2,3,5, 6 of Arm 2 only: creatinine, glucose, potassium, sodium.

c: Every three weeks for both arms: Albumin, alkaline phosphatase, total bilirubin, calcium, creatinine, potassium, SGOT [AST], SGPT [ALT], sodium.

- d: Baseline scans can include either: 1) CT with contrast or MRI of the head and neck region, CT of chest or chest x-ray. Response assessment should include assessment of all sites of disease and use the same imaging method as was used at baseline.
- e: Restaging scans must be repeated after the end of protocol treatment within 8 weeks of completion of radiation. Thereafter, scans of the head and neck will be repeated as clinically indicated, but at a minimum of every 6 months (± 6 weeks) for the first two years. Following this, all scans are at the treating physician's discretion.
- f: Serum pregnancy test (women of childbearing potential).
- g: Pre-study, at 3 months (± 6 weeks) and 12 months (± 12 weeks) following initiation of treatment.
- h: Physical exams will be repeated as clinically indicated, but at a minimum of every 6 months (± 6 weeks) for the first two years. Following this, all follow-up is at the treating physician's discretion.
- i: Only on Days 1 and 2 of cycle 1

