1.2 Secondary Objectives

1.2.1 To compare the following therapeutic endpoints in both populations:

- 2-year local control rates
- Overall survival (OS)
- Progression free survival (PFS)
- Response Rate (Cohort 1 only, as Cohort 2 is completely resected)

1.2.2 To compare and contrast the development of oxidative stress markers which occur as a result of exposure to weekly or every 3-week doses of cisplatin in this population

1.2.3 Rates of radiation related CTCAE adverse events, specifically: mucositis, dysphagia, dry mouth, and skin and their relationships with patient reported outcomes at 3 months and 12 months

1.2.4 CTCAE acute (< 90 days from start of chemoradiation) adverse events related (possibly, probably or definitely) to cisplatin or radiation

- 1.2.5 CTCAE late (> 90 days from start of chemoradiation) adverse events related (possibly, probably or definitely) to cisplatin or radiation.
- 1.2.6 Quality of life as measured by Functional Assessment of Cancer Therapy-Head & Neck (FACTHN) and Functional Assessment of Cancer Therapy Cognition (FACTCOG) at baseline, 3, and 12 months from end of RT

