5.2.2 Cisplatin Dosing

Use the actual body weight as long as the BSA is ≤ 2.3 . If the BSA is > 2.3 , recalculate using the adjusted body weight, and use the recalculated BSA to determine the dose with no cap.

Estimate Ideal body weight in (kg)

Males: IBW = 50 kg + 2.3 kg for each inch over 5 feet

Females: IBW = 45.5 kg + 2.3 kg for each inch over 5 feet

Adjusted body weight

$$AjBW = IBW + 0.4(ABW - IBW)$$

Arm 1 – Conventional fractionation plus every 3-week cisplatin

Patients will receive cisplatin (100 mg/m²) administered intravenously over 1 hour on days 1, 22, and 43 of the treatment course, relative to the initiation of radiation.

Arm 2 – Conventional fractionation plus weekly cisplatin

Patients will receive cisplatin (40 mg/m²) administered intravenously over 1 hour on days 1, 8, 15, 22, 29, 36, and 43 of the treatment course, relative to the initiation of radiation.

Premedication: Arms 1 & 2

Suggested premedication: include aprepitant (intravenous or oral), ondansetron, dexamethasone and either promethazine or prochlorperazine, per institutional standard. This trial endorses the NCCN guidelines for anti-emetic prophylaxis.

Pre- and Post-hydration: Arms 1 & 2

Patients must receive vigorous hydration and diuresis. A suggested regimen is: pre-hydration with a 1 liter of normal saline with electrolyte supplementation (e.g. potassium, magnesium) per standard of care, over 2 hours i.v. immediately prior to cisplatin. Then cisplatin 100 mg/m² in 500 ml normal saline is administered over 1 hour. Following cisplatin infusion, an additional 1 liter of normal saline with electrolyte supplementation (e.g. potassium, magnesium) per standard of care, given post-hydration over 2 hours.

Please see Section 6.0 for all dose modifications of cisplatin.

5.3 **Radiation Therapy**

All radiation therapy is considered standard of care, and toxicities and dose modifications will be made by the treating physician based on institutional standards. The guidelines below are recommended practice but may be modified at the discretion of the treating radiation oncologist.

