Vascular toxicities: Vascular toxicities coincident with the use of CISPLATIN in combination with other antineoplastic agents have been reported. The events are clinically heterogeneous and may include myocardial infarction, cerebrovascular accident, thrombotic microangiopathy (hemolytic-uremic syndrome [HUS]), or cerebral arteritis. Various mechanisms have been proposed for these vascular complications. There are also reports of Raynaud's phenomenon occurring in patients treated with the combination of bleomycin, vinblastine with or without CISPLATIN. It has been suggested that hypomagnesemia developing coincident with the use of CISPLATIN may be an added, although not essential, factor associated with this event. However, it is currently unknown if the cause of Raynaud's phenomenon in these cases is the disease, underlying vascular compromise, bleomycin, vinblastine, hypomagnesemia, or a combination of any of these factors.

Serum Electrolyte Disturbances: Hypomagnesemia, hypocalcemia, hyponatremia, hypokalemia, and hypophosphatemia have been reported to occur in patients treated with CISPLATIN and are probably related to renal tubular damage. Tetany has been reported in patients with hypocalcemia and hypomagnesemia. Generally, normal serum electrolyte levels are restored by administering supplemental electrolytes and discontinuing CISPLATIN. Inappropriate antidiuretic hormone syndrome has also been reported.

Hyperuricemia: Hyperuricemia has been reported to occur at approximately the same frequency as the increases in BUN and serum creatinine. It is more pronounced after doses >50 mg/m², and peak levels of uric acid generally occur between 3 to 5 days after the dose. Allopurinol therapy for hyperuricemia effectively reduces uric acid levels.

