13. STATISTICAL CONSIDERATIONS

13.1 Study Design/Endpoints

This is a 1:1 randomized, unblinded phase II trial of radiation with cisplatin weekly versus every three weeks for patients with locally advanced non-nasopharyngeal SCCHN. The primary endpoint is cisplatin-related acute toxicities (within the first 90 days after the start of radiation). These include all grade 3-5 events of nausea/vomiting, ototoxicity, nephrotoxicity, and neutropenia and thrombocytopenia. Secondary objectives include clinical outcomes (2-year local control rates, OS, PFS, response), additional toxicity outcomes (rates of dysphagia, dry mouth, and skin, other acute and late events according to CTCAE), correlates (oxidative stress markers), and quality of life outcomes (FACTHN, FACTCOG).

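### Magnesium and phosphate losses are named as cisplatin toxicities but are on no itemised chemistry panel, so their incidence will rest on unscheduled tests

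*Combined protocol and SAP*

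**What the plan says.** Section 7.1.1.1 names the toxicities: "Hypomagnesemia, hypocalcemia, hyponatremia, hypokalemia, and hypophosphatemia have been reported to occur in patients treated with CISPLATIN". It regards them as probably due to renal tubular damage and mentions tetany with low calcium and low magnesium. Section 5.2.2 expects some loss to be replaced, since its suggested hydration regimen includes "pre-hydration with a 1 liter of normal saline with electrolyte supplementation (e.g. potassium, magnesium) per standard of care". Magnesium there is an example within a suggestion, not a fixed requirement.

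The Study Calendar (Section 10) itemises two panels. Footnote c applies to both arms: "c: Every three weeks for both arms: Albumin, alkaline phosphatase, total bilirubin, calcium, creatinine, potassium, SGOT [AST], SGPT [ALT], sodium". Footnote b applies to the weekly arm alone: "b: Weeks 2,3,5, 6 of Arm 2 only: creatinine, glucose, potassium, sodium".

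Two other provisions are not itemised. Baseline work-up asks for "serum chemistry tests to include alkaline phosphatase, creatinine, electrolytes, AST (SGOT), and total bilirubin". For a patient whose condition is deteriorating, "laboratory evaluations should be repeated within 48 hours prior to initiation of the next cycle of therapy".

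On the analysis side, secondary objective 1.2.4 covers "CTCAE acute (< 90 days from start of chemoradiation) adverse events related (possibly, probably or definitely) to cisplatin or radiation". Section 7.6 requires all adverse events to be reported apart from a short list of exclusions. Among laboratory abnormalities other than lymphopenia, only grades 1-2 that the treating physician judges clinically unimportant are excused. Section 13.4 promises incidence tables for all toxicity outcomes, and treats secondary endpoints as exploratory and mainly descriptive.

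**The concern.** A laboratory adverse event needs a laboratory value. The plan names low magnesium and low phosphate as cisplatin effects and undertakes to record and tabulate acute cisplatin-related events, but it schedules no on-treatment measurement of either analyte. Whether such an event enters the tables then depends on who orders a test, when and why, and the person ordering knows the arm.

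The trial exists to compare the toxicity of two schedules. At stake is whether the electrolyte rows of the secondary toxicity tables can be read as a comparison, or only as a record of what clinicians happened to look for.

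**Working it through.** **Step 1: named toxicities against itemised panels.** Inputs are the electrolyte paragraph of Section 7.1.1.1 and footnotes b and c of Section 10.

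| Disturbance named in 7.1.1.1 | Footnote c (both arms) | Footnote b (weekly arm only) |
|---|---|---|
| Low sodium | yes | yes |
| Low potassium | yes | yes |
| Low calcium | yes | no |
| Low magnesium | no | no |
| Low phosphate | no | no |

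Footnote c covers 3 of 5 and footnote b covers 2 of 5. Two of 5 are in neither, so scheduled on-treatment measurements of magnesium and phosphate number 0 in each arm.

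**Step 2: scheduled chemistry by arm.** The calendar columns are hard to align in the extracted text, so the weeks are read from the footnotes and the dosing days in Section 5.2.2. Footnote c falls in weeks 1, 4 and 7 in both arms. Footnote b adds weeks 2, 3, 5 and 6 in the weekly arm.

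- Three-weekly arm: sodium and potassium in 3 treatment weeks.
- Weekly arm: sodium and potassium in 3 + 4 = 7 treatment weeks.
- Calcium: 3 treatment weeks in each arm.

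Sodium and potassium are therefore measured in both arms but unequally, while magnesium and phosphate are scheduled in neither arm.

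**Step 3: which endpoint is touched.** Section 13.1 says of the primary endpoint: "These include all grade 3-5 events of nausea/vomiting, ototoxicity, nephrotoxicity, and neutropenia and thrombocytopenia". No electrolyte event is in that list. The sample size in Section 13.2 reproduces from its own inputs and does not involve this point. With 36 per arm, rates of 80% and 50%, and a one-sided Fisher's exact test at 0.05, exact power is 80.9% against the stated 80%. Recruitment is 72 / (1 − 0.10) = 80. Magnesium and phosphate events fall under 1.2.4 and the Section 13.4 tables only.

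**Step 4: size of the remedy.** Footnote c chemistry is drawn at five time points: pre-study, weeks 1, 4 and 7, and post-treatment.

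- Assays of each analyte: 80 × 5 = 400, an upper figure that assumes every patient attends every time point.
- Pre-study and week 1 samples, which serve mainly as baseline: 80 × 2 = 160.
- Samples able to show an on-treatment or post-treatment change: 80 × 3 = 240.

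**The case against.** Several counter-arguments have force.

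- **Events can still be captured.** Adverse events are evaluated throughout treatment, and Section 7.6 makes a clinically significant or grade 3 or higher result reportable whatever prompted the test. A reader might infer that magnesium and phosphate events cannot be detected or counted, or that the Section 13.4 tables would be wrong. The documents do not support that. They support only unscheduled and probably incomplete ascertainment.
- **Bias between arms is not shown.** Seven cisplatin visits against three might suggest 7/3 = 2.3 times the chance of detection in the weekly arm. But Section 5.3.1 brings both arms in for radiation five times a week, 30-35 fractions in all, so opportunity to test does not follow cisplatin visits. Clinicians might equally test more around the larger doses. Neither a ratio nor a direction can be defended. What stands is that testing at the discretion of unblinded staff gives no assurance of comparability.
- **The toxicity list is not an endpoint list.** Section 7.1.1.1 also names raised uric acid and amylase, and the footnotes schedule neither. The protocol never undertook to assay every listed effect. This lowers the severity. It does not remove the gap, because the other three members of the same electrolyte group are scheduled and these two are not.
- **The endpoint is secondary and descriptive.** This is true, and it limits the consequence. A descriptive comparison of arms still needs like-for-like measurement.
- **Scheduled assays do not settle everything.** Under Section 7.6, reporting of grade 1-2 abnormalities would still turn on the treating physician's judgement. Adding the tests makes measurement uniform, but not low-grade reporting or attribution.

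**Conclusion.** The point holds in a limited form and is minor. Two of the five electrolyte disturbances that the protocol attributes to cisplatin have no itemised on-treatment test in either arm. Their incidence under objective 1.2.4 is likely to be understated and may not be comparable between arms, by an amount and in a direction that the documents do not allow one to estimate.

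This rests on reading footnotes b and c as complete lists. It also rests on there being no other protocol-directed magnesium or phosphate test on treatment. The un-itemised baseline electrolytes may or may not include the two analytes, and the un-itemised repeat tests for a deteriorating patient might include them. Neither provides uniform on-treatment measurement.

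A reader might take the acute toxicity objective to mean the primary endpoint. It does not here: this gap leaves the primary endpoint, its power and the sample size unchanged. The weekly arm's extra creatinine tests under footnote b, which bear on nephrotoxicity, are a separate matter.

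**What to change.** 1. Add magnesium and phosphate to the footnote c panel at its existing time points in both arms, and itemise the baseline electrolytes so that a pre-treatment value is certain.
2. In Section 13.4, state that between-arm tables count laboratory electrolyte events from the footnote c time points common to both arms, with results from all other tests listed separately. The same rule handles sodium and potassium (weeks 1-7 in the weekly arm against weeks 1, 4 and 7 in the three-weekly arm).
3. If grade 1-2 electrolyte events are to be compared, grade them from the recorded values, since Section 7.6 otherwise leaves their reporting to the treating physician.

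The cost is a calendar amendment and at most about 400 assays of each analyte on blood already scheduled. No visit or sample-size figure changes. The drawback is a small laboratory expense.

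If the sponsor prefers not to add the tests, the least that is needed is a sentence in Section 13.4 saying that magnesium and phosphate events come only from clinically indicated testing, and that their incidence will be reported with that limitation.
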